7.1. Biomarker Objectives

Inhibition of BTK tyrosine phosphorylation by ibrutinib has been shown to abrogate downstream survival pathways (eg, ERK1/2, PI3K, NF- κ B, and MAPK). Inhibition by ibrutinib also interferes with activation of integrins and chemokine networks leading to interference with adhesion, migration, and homing of malignant cells. It is anticipated that subjects with alterations in BCR-signaling components or activation of alternative signaling pathways may have differential response to treatment.

7.2. Biomarker Analysis Sets

This population consists of all subjects who receive at least 1 dose of study drug (either ibrutinib or nivolumab). Subjects from this population will be analyzed if they received the treatment, have data from at least one of the clinical endpoints and also have data from any biomarkers. The biomarker population is defined as having at least one assay among all the results.

7.3. Biomarker Stratification Groups

Biomarker analysis will be performed with no patient stratification (all patients) and with stratification by dose expansion cohort by indication (i.e., biomarker stratification cohort) as shown:

- A. CLL
- B. CLL only del 17p
- C. CLL only del 11q
- D. FL
- E. DLBCL
- F. ABC-DLBCL (if available)
- G. GCB-DLBCL (if available)
- H. Richter Syndrome
- I. ABC-like Richter's (if available)
- J. GCB-like Richter's (if available)

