1.2.4. Clinical Efficacy of Ibrutinib

The clinical benefit of ibrutinib was first demonstrated in a Phase 1 dose-escalation study of ibrutinib in subjects with recurrent B-cell lymphomas with ORRs ranging from 85.7% in subjects with chronic lymphocytic leukemia/small lymphocytic lymphoma (CLL/SLL) and mantle cell lymphoma (MCL) to 33.3% in subjects with diffuse large B-cell lymphoma (DLBCL). These findings were further demonstrated in subsequent Phase 2 studies in subjects with previously treated MCL or CLL/SLL, and a randomized, comparator-controlled Phase 3 pivotal study in subjects with previously treated CLL/SLL. Activity was also demonstrated in other histologies (follicular lymphoma, Waldenström's macroglobulinemia, marginal zone lymphoma, multiple myeloma) and with combination therapy (fludarabine, cyclophosphamide, rituximab; bendamustine + rituximab; and ofatumumab).

Chronic Lymphocytic Leukemia (CLL)/Small Lymphocytic Lymphoma (SLL)

In the Phase 2 study PCYC-1102-CA, subjects with relapsed or refractory or treatment-naïve CLL/SLL were treated with 420 mg or 840 mg daily continuously until disease progression or until the subject could no longer tolerate the treatment. Ibrutinib produced an overall response rate of 78.4% in 51 subjects with relapsed/refractory disease. Responses were rapid (median of 1.8 months) and durable. Objective responses appeared independent of poor-risk factors including cytogenetics such as deletion of the short arm of chromosome 17 ie, del(17p13.1) or deletion of the long arm of chromosome 11 ie, del(11q21-q23). At Month 24, the proportion of subjects treated with the 420 mg/day dose who were alive and progression-free was 82.3%, and the overall survival rate was 89.6%. The 840 mg dose level did not appear to improve efficacy. Therefore, 420 mg daily dose was chosen as the recommended dose for further development in CLL/SLL.

An analysis of long-term follow-up in subjects with CLL/SLL from the Phase 2 Study 1102 and the 1103 extension study showed that efficacy was sustained over time. Overall response rate (ORR) (per IRC assessment) was 83.9% in treatment-naïve subjects and 76.2% in previously treated subjects. The ORR when including PR-L (per IRC assessment) was 90.3% and 79.2%, respectively. At 30 months, the PFS rate was 96.3% for treatment-naïve subjects and 68.4% for previously treated subjects.

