In a Phase 3 randomized, comparator-controlled, pivotal study in subjects with CLL/SLL (Study 1112), ibrutinib improved efficacy outcomes in subjects with previously treated CLL/SLL compared to that ofatumumab. Analysis of PFS (per the Independent Review Committee [IRC]) demonstrated a statistically significant reduction in the risk of disease progression or death in the ibrutinib arm compared to the ofatumumab arm (HR=0.215, $p<0.0001$). Analysis of OS showed that subjects in the ibrutinib arm had a statistically significant reduction in the risk of death (HR=0.434, $p=0.0049$). The ORR (IRC assessment) was significantly higher ($p<0.0001$) for subjects in the ibrutinib arm (42.6%) than those in the ofatumumab arm (4.1%). The ORR, when including partial response with lymphocytosis (PR-L) (per IRC assessment), was 62.6% for the ibrutinib arm and 4.1% for the ofatumumab arm ($p<0.0001$).

Follicular Lymphoma (FL)

In the Phase I study PCYC-04573, sixteen subjects enrolled to the dose-escalation phase had a diagnosis of FL (Fowler 2012).¹⁸ Eleven subjects received ibrutinib at doses that achieved full BTK occupancy (ie, 2.5 mg/kg or higher). Median time on ibrutinib was 7 months (0 to 29 months) and time to response was 4.6 months. Overall response rate was 54.5% (3 CRs, 2 PRs). Responses were durable (median response duration: 12.3 months). Three patients had chemorefractory disease; 2 of these patients responded (1 CR, 1 PR). On the basis of these very encouraging early efficacy data the single-arm, multicenter Phase 2 study PCI-32765FLR2002 was initiated.

Diffuse Large B-cell Lymphoma (DLBCL)

In a Phase 2 study of ibrutinib in subjects with DLBCL (Study 1106), an interim analysis of response in DLBCL showed an ORR of 25% (CR 9% and PR 16%) with a median time on study of 3.9 months. An analysis of response by molecular subtype demonstrated that subjects with molecular subtype activated B-cell-like (ABC) (non-germinal-cell B-cell-like [GCB]) had an ORR of 41% (CR 17% and PR 24%) and among subjects with the GCB subtype, ORR was 5% (CR 0% and PR 5%).

Richter syndrome

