7.4. Biomarker Tested

- IHC of PDL1, NGS and GEP (if available)

PDL1 protein levels will be examined on tumor cells by Immunohistochemistry (IHC).

FFPE slides from screening will be examined by IHC for PDL1 Staining. Cut points are listed

Biomarker Type	Biomarker	Description	Levels (Cutpoints)	Data column
IHC	PDL1	PDL1 option 1	Not elevated <5% Elevated \geq 5%	PERCENT OF VIABLE TUMOR CELLS THAT EXHIBIT PD-L1 MEMBRANE STAINING
IHC	PDL1	PDL1 option 2	Negative = 0 Positive >0	PERCENT OF VIABLE TUMOR CELLS THAT EXHIBIT PD-L1 MEMBRANE STAINING
NGS	CARD11	Mutation	Positive Negative	
NGS	Additional genes ~5	Mutations	Positive Negative	
GEP (if available)	Genes ~10	Expression	>Median <=Median calculated within disease group	

- T cell Panel

The following flow cytometry T-cell panel will determine a percentage and absolute numbers of each cell type at multiple time points (C1D1, C1D7, C3D1 and End of Treatment (EOT) or Progression (PRO)):

- Absolute lymphocyte counts
- Viable CD3+, % of Single Lymphocytes
- Variable CD3+, Counts
- CD4% of CD3
- CD8% of CD3
- TH17, % of CD4+
- Treg, % of CD4+
- CD4+ICOS+, % of CD4+
- CD4+OX40+, % of CD4+
- CD4+PD-1+, % of CD4+
- CD8+ICOS+, % of CD8+
- CD8+OX40+, % of CD8+

13. CD8+PD-1+, % of CD8+

These values need to be calculated:

14. CD4 Counts

15. Treg Counts

16. TH17 Counts

17. CD4/OX40 Counts

18. CD4/PD-1 Counts

19. CD4/ICOS Counts

20. CD8 Counts

21. CD*/OX40 Counts

22. CD8/PD-1 Counts

23. CD8/ICOS Counts

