7.5.5. Biomarker Data Analysis Methods for PDL1, and NGS and GEP (if available)

- Median, mean (SD), and range for continuous variable or N and frequency (%) for categorical variables will be reported for all-treated versus the biomarker populations for selected demographic and baseline characteristic variables including the biomarker stratification cohorts.
- The number of subjects (N) and the associated percentage (%) will be presented to facilitate the evaluation of the response rate. The median duration of response (arising from Kaplan-Meier estimate) between 1) PDL1 IHC option 1/2 subgroups (i.e., not elevated/negative vs. elevated/positive); 2) NGS subgroups (i.e., negative vs. positive); 3) GEP subgroups (i.e., >median vs. <=median) will also be reported.

The relationship between 1) PDL1 not elevated (or negative) vs. elevated (or positive) subgroups; 2) NGS negative vs. positive subgroups; 3) GEP subgroups >median vs. <=median subgroup for duration of response, progression-free survival and overall survival will be evaluated by the Kaplan-Meier method. If the number of subjects is ≤ 7 then Kaplan-Meier analyses are unnecessary.

- For each of the biomarker stratification cohort, Fisher exact test will be used to test the association on the response between 1) PDL1 subgroups (not elevated and elevated for option 1; negative and positive for option 2); 2) NGS subgroups (negative vs. positive); 3) GEP subgroups (>median vs. <=median)
- Descriptive summary statistics [i.e., mean (SD), median and range] will be used to evaluate time to initial response and best response of the PDL1, NGS and GEP subgroups for each of the biomarker stratification cohort.

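### The SAP's all-patients biomarker comparison of PD-L1 and mutation subgroups has no disease adjustment and unclear scope, so a marker that only tracks disease type could look predictive

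*SAP*

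**What the plan says.** SAP 7.3 sets two levels of analysis: "Biomarker analysis will be performed with no patient stratification (all patients) and with stratification by dose expansion cohort by indication". It calls the by-indication groups the biomarker stratification cohorts and lists them as CLL, FL, DLBCL and Richter syndrome, with deletion and cell-of-origin subsets.

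SAP 7.4 defines the marker subgroups. PD-L1 is read from one data column ("PERCENT OF VIABLE TUMOR CELLS THAT EXHIBIT PD-L1 MEMBRANE STAINING") and cut at 5% or at 0, whatever the disease. CARD11 and about five further genes are called positive or negative. Only the gene-expression median is "calculated within disease group".

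SAP 7.5.5 gives the methods. For response: "For each of the biomarker stratification cohort, Fisher exact test will be used to test the association on the response between" the marker subgroups. For the time-to-event endpoints, the marker subgroups "for duration of response, progression-free survival and overall survival will be evaluated by the Kaplan-Meier method". That paragraph names no cohort, stratification factor, log-rank test or Cox model. Protocol 12.6 names ANOVA, categorical and survival models, also without a disease term.

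**The concern.** Confounding by disease needs two things: an outcome that differs by disease and a marker whose frequency differs by disease.

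The protocol's own background supplies the first. In CLL/SLL, "Ibrutinib produced an overall response rate of 78.4% in 51 subjects with relapsed/refractory disease"; in DLBCL, "an interim analysis of response in DLBCL showed an ORR of 25" percent. SAP 1.2 expects median treatment of 2 months in DLBCL and 15 months in CLL.

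The second is possible for PD-L1 and mutations, because one rule is applied across all diseases. In the pooled set, marker-positive and marker-negative subjects may then differ mainly in their disease mix. A marker with no effect in any disease could look predictive, and a real effect could be hidden. Protocol 12.6 gives the identification of responsive or resistant subgroups as the purpose of this work, so a spurious marker would bear directly on it.

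**Working it through.** **The plan's own figure.** The documents give no operating characteristics for the biomarker analysis. The nearest figure is the Part B cohort size. With n = 32 and success at 10 or more responses, the exact binomial gives alpha 0.0898 at 20% and power 0.833 at 38%; n = 31 gives power 0.799. So 32 reproduces. The 35 enrolled per cohort is used below, and Part A subjects are left out.

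**Inputs from protocol 1.2.4 (single-agent ibrutinib).**
- CLL/SLL: 78.4% (Phase 2), or 42.6%, 62.6% counting PR with lymphocytosis (Phase 3).
- FL: 54.5% as printed. The counts beside it, 3 CR + 2 PR among the 11 subjects treated at full-occupancy doses, give 5/11 = 45.5%. Both are used.
- DLBCL: 25%.

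**Assumed inputs.**
- Richter response rate 33%. The single-agent data are 3 responders among 3 evaluable, too few to use.
- Marker prevalence in CLL/FL/DLBCL/Richter: 20/20/40/40%, 10/20/40/50% and 10/10/50/50%, with equal prevalence as the control.
- A marker result for all 35 subjects in each cohort.

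**Expected pooled response rates for a null marker.** With prevalence p_k and response rate r_k in disease k:

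ORR+ = Σ p_k r_k / Σ p_k, and ORR− = Σ (1−p_k) r_k / Σ (1−p_k).

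Rates 78.4/54.5/25/33, prevalence 10/10/50/50:
- ORR+ = (7.84 + 5.45 + 12.5 + 16.5)/1.2 = 35.2%
- ORR− = (70.56 + 49.05 + 12.5 + 16.5)/2.8 = 53.1%

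Same rates, prevalence 20/20/40/40:
- ORR+ = (15.68 + 10.9 + 10 + 13.2)/1.2 = 41.5%
- ORR− = (62.72 + 43.6 + 15 + 19.8)/2.8 = 50.4%

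These gaps of about 18 and 9 points come from disease mix alone. With CLL 42.6% and FL 45.5%, the 10/10/50/50 pattern gives 37.81/1.2 = 31.5% against 108.29/2.8 = 38.7%, a gap of about 7 points.

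**False-positive rate.** Simulation of 4 × 35 subjects, marker independent of response within each disease. The pooled two-sided Fisher test at 0.05 is compared with CMH stratified by disease:

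z = Σ(a_k − M_k R_k/n) / √[Σ M_k(n−M_k)R_k(n−R_k)/(n²(n−1))],

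where a_k, M_k and R_k are the marker-positive responders, marker-positives and responders in disease k, and n = 35.

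| CLL / FL rate | Pooled Fisher, unequal prevalence | Disease-stratified CMH |
|---|---|---|
| 78.4% / 54.5% | about 14-46% | near 5% |
| 62.6% / 45.5% | about 9-23% | near 5% |
| 42.6% / 45.5% | about 5-10% | near 5% |

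Each range runs from the 20/20/40/40 to the 10/10/50/50 pattern; in the first row the middle pattern gives 31%. With equal prevalence the pooled test does not exceed 5%.

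**On the SAP's own test scale.** SAP 7.5.1 specifies one-sided tests at 0.025 without stating a direction. With rates 78.4/54.5/25 and Richter at 25%, the pooled Fisher test rejects in 14.5% (20/20/40/40) and 51% (10/10/50/50) in the tail where marker-positive looks worse. CMH gives 2.2-2.7%. A split at the within-disease median, as for gene expression, gives 0.8-1.5% across the rate sets in which diseases differ, so it is not inflated.

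**Kaplan-Meier.** No test is named, so only the display can be examined. Take 15 months (CLL) and 2 months (DLBCL) from SAP 1.2 as stand-in medians m_k, assume 8 (FL) and 2 (Richter) with exponential times, and use prevalence 10/20/40/50. Solving Σ p_k exp(−t ln2/m_k)/Σ p_k = 0.5, and the same with 1−p_k, gives pooled medians of 2.7 months (marker-positive) and 5.2 months (marker-negative). With equal prevalence the two coincide.

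**The case against.** The strongest objection is textual. A reader who sees only the words "Fisher exact test will be used to test the association on the response between" might infer that the SAP prespecifies a pooled Fisher test. The sentence opens by limiting the test to each biomarker stratification cohort, which 7.3 defines by indication. A pooled Fisher test therefore rests only on the general statement in 7.3. This stands, and it means the rejection rates above describe a test that the SAP may or may not intend.

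It also stands that Kaplan-Meier estimation without a named test has no p-value to inflate. The harm there is misleading curves and medians.

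The inputs are open to challenge too. The response rates are for ibrutinib alone, not the combination. Every unequal prevalence pattern puts the marker lowest where response is highest. On a one-sided test in the opposite direction, those patterns almost never reject. Fewer marker results would also reduce the inflation: at an assumed 20 per disease, the one-sided rate for the 10/20/40/50 pattern falls from 28% to 16%. All of this limits the size. It does not remove the mechanism, and the tail would switch for a marker commoner in the high-response diseases.

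Finally, the work is exploratory, p-values are nominal (SAP 7.5.1), protocol 10.5 allows the analyses to be deferred or dropped, and by-indication results are planned. This justifies a low severity. By-indication results are only a weak check, however: at about 35 subjects or fewer, a negative result cannot separate confounding from low power.

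**Conclusion.** The point holds as a minor one. The SAP commits to an unstratified all-patients biomarker analysis. For PD-L1 and mutation subgroups it provides no protection against confounding by disease, and 7.3 and 7.5.5 leave unclear whether response is tested in the pooled set.

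If it is tested, the two-sided 0.05 error rate for a null marker ranges from no inflation (equal prevalence) to about 46% (strongly unequal prevalence with the highest cited CLL and FL rates). The range rests on assumed prevalences, an assumed Richter rate of 33%, single-agent response rates and 35 marker results per cohort. No single figure in it should be quoted as the trial's error rate.

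Two stronger readings are not supported. One is that all planned biomarkers are affected: gene expression is cut within disease and is not. The other is that the time-to-event comparisons carry an inflated p-value: none is specified.

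**What to change.** Reconcile SAP 7.3 and 7.5.5 by stating which methods apply to the all-patients set. For any all-patients comparison of PD-L1 or mutation subgroups, specify stratification by disease: CMH or exact conditional logistic regression for response, and a disease-stratified log-rank test or Cox model for DOR, PFS and OS. State that any unstratified pooled table or curve is descriptive only and carries no p-value. The by-indication analyses stay as written.

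The cost is a few lines of SAP wording and a stratification option in the program. No data are lost and no new data are needed.

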7.4. Biomarker Tested

- IHC of PDL1, NGS and GEP (if available)

PDL1 protein levels will be examined on tumor cells by Immunohistochemistry (IHC).

FFPE slides from screening will be examined by IHC for PDL1 Staining. Cut points are listed

Biomarker Type	Biomarker	Description	Levels (Cutpoints)	Data column
IHC	PDL1	PDL1 option 1	Not elevated <5% Elevated \geq 5%	PERCENT OF VIABLE TUMOR CELLS THAT EXHIBIT PD-L1 MEMBRANE STAINING
IHC	PDL1	PDL1 option 2	Negative = 0 Positive >0	PERCENT OF VIABLE TUMOR CELLS THAT EXHIBIT PD-L1 MEMBRANE STAINING
NGS	CARD11	Mutation	Positive Negative	
NGS	Additional genes ~5	Mutations	Positive Negative	
GEP (if available)	Genes ~10	Expression	>Median <=Median calculated within disease group	

- T cell Panel

The following flow cytometry T-cell panel will determine a percentage and absolute numbers of each cell type at multiple time points (C1D1, C1D7, C3D1 and End of Treatment (EOT) or Progression (PRO)):

- Absolute lymphocyte counts
- Viable CD3+, % of Single Lymphocytes
- Variable CD3+, Counts
- CD4% of CD3
- CD8% of CD3
- TH17, % of CD4+
- Treg, % of CD4+
- CD4+ICOS+, % of CD4+
- CD4+OX40+, % of CD4+
- CD4+PD-1+, % of CD4+
- CD8+ICOS+, % of CD8+
- CD8+OX40+, % of CD8+

13. CD8+PD-1+, % of CD8+

These values need to be calculated:

14. CD4 Counts

15. Treg Counts

16. TH17 Counts

17. CD4/OX40 Counts

18. CD4/PD-1 Counts

19. CD4/ICOS Counts

20. CD8 Counts

21. CD*/OX40 Counts

22. CD8/PD-1 Counts

23. CD8/ICOS Counts

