12.6. Biomarker Analyses

Analyses are planned to identify biomarkers that are indicative of the mechanisms of action of the drug or predictive of efficacy for the combination. The associations of biomarkers with clinical response or time-to-event endpoints will be assessed using the appropriate statistical methods (analysis of variance [ANOVA], categorical, or survival model), depending on the endpoint. Correlation of baseline expression levels or changes in expression levels with response or time-to-event endpoints will identify responsive (or resistant) subgroups.

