1.4. Sample Size Justification

The sample size is calculated based on the following assumptions:

- The overall response rate under null hypothesis is 20%
- The overall response rate under alternative hypothesis is at least 38%
- The probability to mistakenly rejecting the null hypothesis when it is actually true is 0.1 (one-sided).
- The probability to correctly rejecting null hypothesis when alternative hypothesis is true is at least 0.8

Under the above assumptions, the study will enroll approximately 35 subjects to get at least 32 response evaluable subjects in each cohort of Part B (Cohorts B1, B2, B3, and B4).

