7.5.1. Level of Significance

All tests will be 1-sided. The primary efficacy endpoint will be tested at the overall significance level of 0.025. Nominal p-values will be presented for all statistical analyses, if applicable.

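### The SAP analyses gene expression only as a within-disease median split; making the measured value the main exploratory analysis would recover information that small cohorts can ill afford to lose

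*SAP*

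**What the plan says.** SAP 7.4 lists gene expression profiling as about 10 genes, if available, with one coding: ">Median <=Median calculated within disease group".

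SAP 7.5.5 carries that two-level variable through every analysis.
- **Response:** "Fisher exact test will be used to test the association on the response between" the subgroups, within each biomarker stratification cohort.
- **DOR, PFS and OS:** the two groups "for duration of response, progression-free survival and overall survival will be evaluated by the Kaplan-Meier method". No log-rank test or Cox model is named.
- **Time to initial and best response:** descriptive statistics by subgroup.

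SAP 7.5.1 sets the level: "All tests will be 1-sided. The primary efficacy endpoint will be tested at the overall significance level of 0.025", with nominal p-values. SAP 7.5.3 permits a log transformation of biomarker data, and SAP 7.5.4 rules out any outlier handling.

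Protocol 12.6 lists ANOVA, categorical and survival models, according to the endpoint, and adds "Correlation of baseline expression levels or changes in expression levels with response or time-to-event endpoints" as the route to responsive or resistant subgroups.

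**The concern.** A median split treats a subject just above the cut like the highest expresser, and one just below it like the lowest. In a large study that waste may be tolerable. Here SAP 1.4 plans "approximately 35 subjects to get at least 32 response evaluable subjects" per Part B cohort, and the del 17p, del 11q, ABC and GCB strata in SAP 7.3 are smaller still.

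The log transformation allowed in SAP 7.5.3 cannot help, because a median split is unchanged by any monotone transformation. The SAP does keep other biomarkers on their measured scale: SAP 7.5.6 analyses the T-cell panel through means and paired t-tests.

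At stake is the exploratory aim of finding markers of response or resistance. A real association could be missed in samples that were able to show it.

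**Working it through.** **1. The plan's own sample size.** Inputs from SAP 1.4: ORR 20% against 38%, one-sided alpha 0.1, power at least 0.8. The exact binomial rule of 10 or more responses in 32 has alpha 0.0898 and power 0.833. At n = 31 power is 0.799, so 32 is the smallest n that meets both limits. The figure reproduces, but it concerns ORR only. The documents give no power for the expression analysis.

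**2. Information kept by a median split.** For a normal variable, the correlation with its own above/below-median indicator is √(2/π) = 0.798. The efficiency for a small linear effect is its square, 2/π = 0.637. So 35 subjects act like 35 × 0.637 = 22.3, and 32 act like 32 × 0.637 = 20.4.

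**3. Power for response.** The responder counts follow the design rates: 0.38 × 35 = 13.3, taken as 13, and 0.20 × 35 = 7. Simulation used 4,000 data sets per setting, with normal expression shifted upward in responders.

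| Responders of 35 | Shift | Level | Median split, Fisher | Measured value, Wilcoxon |
|---|---|---|---|---|
| 13 | 1.0 SD | two-sided 0.05 | 50% | 77% |
| 13 | 0.8 SD | two-sided 0.05 | 33% | 58% |
| 7 | 1.0 SD | two-sided 0.05 | 52% | 60% |
| 7 | 1.0 SD | one-sided 0.025 (SAP level) | 16% | 60% |

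**4. Why the last two rows differ.** With 35 subjects, 17 lie above the median and 18 at or below it. Let X be the number of the 7 responders who lie above. Under no association:
- P(X = 7) = 19,448 / 6,724,520 = 0.0029
- P(X ≥ 6) = (222,768 + 19,448) / 6,724,520 = 0.036

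At one-sided 0.025 only 7 of 7 is significant. Two-sided, 6 of 7 gives 0.036 + 31,824 / 6,724,520 = 0.041 and passes at 0.05. The fall from 52% to 16% is therefore discreteness of the exact test, not the split itself.

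**5. Separating the two causes.** A second simulation (6,000 data sets, n = 35, ORR 38% with the responder count left random, 1 SD, one-sided 0.025) gave:
- measured value, t-test: 78.6% (Wilcoxon 76.1%)
- median split, uncorrected score test: 56.4%
- median split, Fisher: 42.6%

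The split costs 78.6 − 56.4 = 22.2 points and Fisher a further 56.4 − 42.6 = 13.8, for a total of 36.0. Fisher's actual size in this setting was about 0.9% against a nominal 2.5%.

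**6. Time-to-event endpoints.** The SAP names no test, so this compares a log-rank score test on the split with a Cox score test on the measured value, at n = 35 and one-sided 0.025. Event counts and hazard ratios are assumed.

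| Events | Log HR per SD | Median split | Measured value |
|---|---|---|---|
| 24 | 0.6 | 56% | 77% |
| 24 | 0.5 | 44% | 64% |
| 18 | 0.6 | 46% | 66% |

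**The case against.** The strongest reply is that Protocol 12.6 lists categorical methods and speaks of identifying subgroups, so a grouped analysis is within its terms. That stands. A reader might infer that the SAP contradicts the protocol; it does not. It leaves out the correlation with expression levels that the protocol also describes.

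Second, the response figures mix two causes. That also stands: step 5 gives about 22 of 36 points to the split and the rest to Fisher, and with 7 responders the two-sided gap is only 8 points. Reading the whole gap as the price of dichotomising would be wrong.

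Third, effect size, normality and monotonicity are assumed. If the true effect were a step at the median, the split would lose nothing.

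Fourth, a median split is robust to extreme values, whereas Cox slopes are not, and SAP 7.5.4 plans no outlier handling. In the smaller strata such slopes could be unstable. This limits where Cox should be used. It does not touch Wilcoxon for response.

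A reader might also object that the cut-off moves between diseases, so that high expression is not comparable. The remedy does not cure this: Wilcoxon ranks within the cohort, and a per-SD slope depends on the cohort's own SD. The point therefore does not rest on comparability.

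**Conclusion.** The concern holds as an inexpensive improvement to an exploratory analysis. Under a monotone effect and roughly normal expression, the median split keeps about 64% of the information. For response, Fisher's conservatism adds to the loss, giving about 50% against 77% power at a 1 SD shift with 13 of 35 responders.

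The cohort size of 35 is a guide. Expression data are conditional on availability, SAP 2.1 may pool Parts A and B within a disease, and several strata are smaller.

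Two stronger readings are not supported. The SAP formally tests expression against response only; for DOR, PFS and OS it plans curves without a test. Nor is the primary result at risk: p-values here are nominal, Protocol 10.5 lets biomarker work be deferred or dropped, and ORR, safety and dose selection do not depend on it.

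**What to change.** In SAP 7.5.5, make log2 expression on its measured scale the main analysis for each gene:
- **Response:** Wilcoxon rank-sum test between responders and non-responders.
- **DOR, PFS and OS:** Cox regression on log2 expression where events suffice, with a check of functional form and of influential values. State in advance the minimum number of events, and omit the model in very small strata. SAP 7.5.5 already drops Kaplan-Meier analyses at 7 or fewer subjects.
- **Display:** keep the within-disease median split for Kaplan-Meier plots and descriptive tables.

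The cost is SAP wording and a little programming on the same samples and software. The small downside is the sensitivity of Cox slopes to extreme values and functional form, which the checks and the event minimum are there to contain.
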